2.0 ENROLLMENT PROCEDURES

2.1 ELIGIBILITY CRITERIA

- 2.1.1 INCLUSION CRITERIA
 - 2.1.1.1 Age: ≥3 years and ≤25 years of age
- 2.1.1.2 Diagnosis: Patients with NF1 and progressive plexiform neurofibromas that have the potential to cause significant morbidity, such as (but not limited to) head and neck lesions that could compromise the airway or great vessels, brachial or lumbar plexus lesions that could cause nerve compression and loss of function, lesions that could result in major deformity (e.g., orbital lesions), lesions of the extremity that cause limb hypertrophy or loss of function, and painful lesions. Histologic confirmation of tumor is not necessary in the presence of consistent clinical and radiographic findings, but should be considered if malignant degeneration of a plexiform neurofibroma is clinically suspected. In addition to plexiform neurofibroma(s), all study subjects must have at least one other diagnostic criteria for NF1 listed below (NIH Consensus Conference[9]):
 - 1. Six or more café-au-lait spots (≥0.5 cm in prepubertal subjects or ≥1.5 cm in postpubertal subjects)
 - 2. Freckling in the axilla or groin
 - 3. Optic glioma
 - 4. Two or more Lisch nodules
 - 5. A distinctive bony lesion (dysplasia of the sphenoid bone or dysplasia or thinning of long bone cortex)
 - 6. A first degree relative with NF1

In this study a plexiform neurofibroma is defined as a neurofibroma that has grown along the length of a nerve and may involve multiple fascicles and branches. A spinal plexiform neurofibroma involves two or more levels with connection between the levels or extending laterally along the nerve.

2.1.1.3 Measurable disease: Patients must have measurable plexiform neurofibroma(s). For the purpose of this study a measurable lesion will be defined as a

lesion of at least 3 cm measured in one dimension. There must be evidence of recurrent or progressive disease as documented by an increase in size or the presence of new plexiform neurofibromas on MRI. Progression at the time of study entry is defined as:

- A measurable increase of the plexiform neurofibroma (≥ 20% increase in the volume, or a ≥ 13% increase in the product of the two longest perpendicular diameters, or a ≥ 6% increase in the longest diameter) over the last two consecutive scans (MRI or CT), or over the time period of approximately one year prior to evaluation for this study.
- Patients who underwent surgery for a progressive plexiform neurofibroma will be eligible to enter the study after the surgery, provided the plexiform neurofibroma was incompletely resected and is measurable.
- 2.1.1.4 Prior therapy: Patients with NF1 are eligible at the time of recurrence or progression of inoperable plexiform neurofibroma.

A surgical consultation should be obtained prior to enrollment on the study to evaluate if tumor resection is a feasible option. Patients will only be eligible if complete tumor resection is not feasible, or if a patient with a surgical option refuses surgery.

Since there is no standard effective chemotherapy for patients with NF1 and progressive plexiform neurofibromas, patients may be treated on this trial without having received prior therapy.

Patients must have recovered from the toxic effects of all prior therapy before entering this study. The Cancer Therapy Evaluation Program Common Toxicity Criteria (CTC) Version 2.0 will be used for toxicity assessment. A copy of the CTC version 2.0 can be downloaded from the CTEP home page at http://ctep.cancer.gov. Recovery is defined as a toxicity grade <2, unless otherwise specified in the Inclusion and Exclusion Criteria.

Patients must have had their last dose of radiation therapy at least six weeks prior to study entry, and their last dose of chemotherapy at least four weeks prior to study entry. Patients who received G-CSF after the prior cycle of chemotherapy must be off G-CSF for at least one week prior to entering this study.

2.1.1.5 Performance Status: Patients should have a life expectancy of at least 12 months and an ECOG performance score of 0, 1, or 2 (see below). Patients who are wheelchair bound because of paralysis should be considered "ambulatory" when they are up in their wheel chair.

\mathbf{F}	D (C = 1
F.U.U.U.T	Performance	Status

Score	Clinical Status
0	Asymptomatic
1	Symptomatic, fully ambulatory
2	Symptomatic, in bed < 50% of the day
3	Symptomatic, in bed > 50% of the day but not bedridden
4	Bedridden

- 2.1.1.6 Hematologic Function: Patients must have an absolute granulocyte count $\geq 1,500/\mu L$, a hemoglobin ≥ 9.0 gm/dl, and a platelet count $\geq 150,000/\mu L$ at study entry, and a normal fibrinogen.
- 2.1.1.7 Hepatic Function: Patients must have a bilirubin within normal limits and SGPT \leq 2x upper limit of normal. Patients with Gilbert syndrome are excluded from the requirement of a normal bilirubin. (Gilbert syndrome is found in 3-10% of the general population, and is characterized by mild, chronic unconjugated hyperbilirubinemia in the absence of liver disease or overt hemolysis).
- 2.1.1.8 Renal Function: Patients must have an age-adjusted normal serum creatinine (see table below) OR a creatinine clearance \geq (70 mL/min/1.73 m²).

Age (Years)	Maximum Serum Creatinine (mg/dl)
≤ 5	0.8
$5 < age \le 10$	1.0
$10 < age \le 15$	1.2
> 15	1.5

- 2.1.1.9 Informed Consent: All patients or their legal guardians (if the patients is <18 years old) must sign an IRB approved document of informed consent (screening protocol) prior to performing studies obtained exclusively to determine patient eligibility. After confirmation of patient eligibility all patients or their legal guardians must sign the protocol specific informed consent to document their understanding of the investigational nature and the risks of this study before any protocol related studies are performed (other than the studies which were performed to determine patient eligibility). When appropriate pediatric patients will be included in all discussion. Per institutional guidelines, age appropriate assent forms for children from 7 through 12 years, and for children may be developed and, when appropriate, will be signed by the pediatric patients in order to obtain written assent.
- 2.1.1.10 Durable Power of Attorney (DPA): All patients ≥18 years of age will be offered the opportunity to assign DPA so that another person can make decisions about their medical care if they become incapacitated or cognitively impaired.

2.1.1.11 Ability to undergo MRI examinations.

2.1.2 EXCLUSION CRITERIA

- 2.1.2.1 Pregnant or breast feeding females are excluded, because the toxic effects and pharmacology of R115777 in the fetus and newborn are unknown.
- 2.1.2.2 Clinically significant unrelated systemic illness (serious infections or significant cardiac, pulmonary, hepatic or other organ dysfunction) which in the judgment of the Principal or Associate Investigator would compromise the patient's ability to tolerate R115777 or are likely to interfere with the study procedures or results.
 - 2.1.2.3 Prior treatment with >1 prior myelosuppressive chemotherapy regimen.
 - 2.1.2.4 An investigational agent within the past 30 days.
- 2.1.2.5 Evidence of an optic glioma, malignant glioma, malignant peripheral nerve sheath tumor or other cancer requiring treatment with chemotherapy or radiation therapy.
- 2.1.2.6 Ongoing radiation therapy, chemotherapy, hormonal therapy directed at the tumor, or immunotherapy.
- 2.1.2.7 Inability to return for follow-up visits or obtain follow-up studies required to assess toxicity and response to therapy.
 - 2.1.2.8 Prior treatment with R115777.

2.2 Pre-Treatment Evaluation (See Appendix 7)

Pre-treatment blood tests should be performed within 2 weeks prior to enrollment on the trial unless otherwise stated. The evaluation required prior to starting treatment phase "A" and "B" is listed in table form in Appendix 7.

2.2.1 History and Physical Examination: Complete history (including prior and concurrent therapy), physical examination including documentation of measurable disease, performance status, and signs and symptoms. A complete neurologic examination should be performed and focus on signs of sensory peripheral neuropathy. Height, weight and body surface area must be recorded. History and physical examination will be documented in case report forms as outlined Section 5.1.1. The BSA should be calculated from the average of 3 repeated measurements of weight and height on the same day using the formula below or a formula used at a participating institution:

$$BSA = \frac{Weight \ (kg)^{0.425} \bullet Height \ (cm)^{0.725}}{139.315}$$

2.2.2 Photography: When possible, plexiform neurofibromas that are visible on the body surface should be photographed prior to treatment with R115777 and placebo. A size marker should be taped to the skin in the field of view when appropriate, and

the plexiform neurofibroma should be photographed so that it fills the frame. Frontal and side images will be taken, as appropriate. Copies of photographs should be sent to the study coordinator, identified by the subject ID number, date, and treatment phase ("A" or "B") and treatment cycle number.

- 2.2.3 HEMATOLOGY: Complete blood counts, differential, platelet count, PT, PTT and fibrinogen.
- 2.2.4 CHEMISTRIES: Electrolytes (including calcium, phosphorus and magnesium), creatinine, SGPT, and bilirubin.
 - 2.2.5 URINALYSIS
 - 2.2.6 URINE PREGNANCY TEST: For all females of child-bearing potential.
- 2.2.7 RADIOGRAPHIC EVALUATION (APPENDIX 1): MRI scan of the progressing plexiform neurofibroma(s) within 2 weeks prior to enrollment on study. In addition, if possible, MRI scan of all known additional, measurable plexiform neurofibroma(s) within 2 weeks of enrollment on study. The progressing plexiform neurofibroma(s) will be identified as index lesion(s), and will be studied by 3-D MRI. Should there be more than 3 progressing plexiform neurofibromas, the three most clinically relevant plexiform neurofibromas will be followed by 3-D MRI analysis. The imaging protocol outlined in Appendix 1 will be used each time MRI examinations are performed to assess the effect to R115777.
- 2.2.8 OPHTHALMOLOGIC EVALUATION: Ophthalmologic examination prior to or within the first three days of starting treatment with R115777 or placebo, including visual fields if the patient is able to cooperate with the exam and examination of the lens for opacifications.
- 2.2.9 TISSUE PROCUREMENT: In patients with easily accessible discrete neurofibromas or superficial plexiform neurofibromas, who consent to the procedure, biopsies will be performed prior to the first dose of treatment at study entry. In addition, attempts will be made to obtain tumor specimens from any patients requiring surgery for complications of their tumors or for unrelated medical problems. Peripheral blood mononuclear cells for FPTase assay (Section 2.2.10, Appendix 5) should be obtained at the same time as biopsy whenever possible. As this is an invasive procedure, patients may refuse biopsy and still be eligible for the study.

Kits will be supplied for handling and shipping of tumor specimens. To obtain a kit, please call [name] at [contact] seven days prior to the planned surgery (Appendix 3, Appendix 4). Two kits will be sent by FedEx to arrive several days prior to the surgical procedure. Included in the kits will be all media and tubes needed for shipment. Procedures for tissue handling and shipment are provided in Appendices 3 and 4, respectively.

2.2.10 FARNESYL-PROTEIN TRANSFERASE (FPTase) ACTIVITY IN PERIPHERAL BLOOD MONONUCLEAR CELLS (PBMC): Peripheral blood mononuclear cells (PBMC) will be

collected pretreatment. The activity of FPTase will be measured in these samples as a surrogate for tumor FPTase inhibition. If the patient has consented to a tumor biopsy, PBMCs should be obtained at the same time as the biopsy (Section 2.2.9). PBMC should be separated from 20 ml of heparinized blood (10 ml in children \leq 10 kg) as described in Appendix 5.

- 2.2.11 NERVE GROWTH FACTOR (NGF): A blood sample will be collected pretreatment. NGF levels will be correlated with the development of clinical neurotoxicity (Appendix 6).
- 2.2.12 QUALITY OF LIFE (QOL) ASSESSMENT: The National Institutes of Health (NIH) Impact of Pediatric Illness (IPI) Scale, which assesses the impact of disease and treatment on children's behavior, should be administered to all patients $\geq 6 \leq 18$ years of age and their primary caregiver prior to the start of therapy. This assessment consists of an age-appropriate questionnaire and generally takes less than 30 minutes to complete. Patients between the ages of 6 and 10 years of age should be administered the IPI-Young Child form; patients between 11 and 18 years of age should be administered the IPI-Older Child/Adolescent form; the patient's primary caregiver should receive the IPI-Parent Form. This questionnaire will not be administered to patients ≥ 18 years.

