Four patients with NF1 continue to receive R115777 on the 21 day schedule after a median of 19 (range 18-23) cycles, and 3 patients with NF1 continue to receive R115777 on the continuous dosing schedule after a median of 11 cycles (range 4-13). Peripheral neuropathy has not been observed in this trial. However, because of the development of peripheral neuropathy in adults, who were treated on the continuous dosing schedule, the 21 day schedule followed by a 7 day rest period will be used in future trials with R115777.

Leukemia Phase I: A phase I trial of R115777 for children with refractory leukemias is ongoing. Twenty children with refractory ALL (n=11), AML (n=8), or JMML (n=1) were treated. Overall, R115777 has been well tolerated. At the starting dose (300 mg/m² q12h po x 21 d, repeated q28 d), 3 of 6 evaluable patients had grade 3 adverse events (AE), which included rash (n=1), hyperbilirubinemia and AST (n=1). The dose was de-escalated to 200 mg/m², and 2 of 6 evaluable patients developed grade 3 AE, which included mucositis (n=1), hyperbilirubinemia (n=1). Two of the three patients who developed grade 3 hyperbilirubinemia, had a history of hyperbilirubinemia during the days preceding treatment with R115777, but normal or grade 1 bilirubin immediately prior to R115777. After discontinuation of R115777, bilirubin remained elevated in one patient, continued to increase in one patient, and decreased to grade 1 toxicity in one patient. The relationship of the study drug to this AE, and of the dose of study drug to this AE are thus unclear.

The protocol was amended to only allow entry of patients with normal liver function tests at trial entry (normal bilirubin, AST, and ALT). Currently, the 300 mg/m² dose level is expanded to enroll up to 12 evaluable patients.

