3.0 IMPLEMENTATION OF STUDY

3.1 STUDY DESIGN

3.1.1 RANDOMIZED DESIGN

This is a randomized, cross-over, double-blinded, placebo-controlled pediatric phase II trial of oral R115777 in children and young adults with NF1 who have progressive plexiform neurofibroma(s). Patients will be randomized to either receive R115777 or placebo first. After documentation of progressive disease on the first treatment, patients will be crossed over to receive R115777 (if placebo was first given) or placebo (if R115777 was first given). The first treatment that a patient is randomized to receive (either placebo or R115777) is defined as "phase A", and the second treatment (either placebo or R115777), is defined as "phase B". There should be a 2 week washout period, during which no drug is administered, when crossing over from the first (phase A) to the second (phase B) treatment. The treatment cycle number will reset to "1" when the patient crosses over from "phase A" to "phase B". For study purposes "arm 1" is defined as treatment with R115777 first followed by placebo, and "arm 2" is defined as treatment with placebo first followed by R115777.

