3.4 ON STUDY EVALUATION (SEE APPENDIX 7)

- 3.4.1 HISTORY & PHYSICAL EXAMINATION: Every 2 weeks during the first 3 cycles on each treatment phase ("A", "B"). Physical exam should include assessment of performance status (documentation if changed from baseline), measurement of visible or palpable neurofibroma, height, weight and body surface area prior to every treatment cycle. A complete neurologic examination should be performed and focus on signs of sensory peripheral neuropathy. After cycle 3 perform prior to each cycle. History and physical examination will be documented in case report forms as outlined Section 5.1.1.
- 3.4.2 Photography: When possible, plexiform neurofibromas that are visible on the body surface should be photographed prior to treatment cycle 1, 4, 7, 10, and then after every 6 cycles on each treatment phase ("A", "B"). A size marker should be taped to the skin in the field of view when appropriate, and the plexiform neurofibroma will be photographed so that it fills the frame. Frontal and side images will be taken, as appropriate. Copies of photographs identified by the patient ID number, date, treatment phase ("A" or "B"), and treatment cycle should be sent to:

[name], R.N.
Pediatric Oncology Branch, NCI
[name]
[name]
Bethesda, MD 20892-1928

3.4.3 LABORATORY ASSESSMENT (see Appendix 7). Laboratory studies will be documented in case report forms as outlined Section 5.1.1.

Hematology: During the first 3 cycles of treatment on each treatment phase ("A", "B"), obtain complete blood count, differential and platelet count every other week (more frequent monitoring may be performed if the ANC <1,000/mm³ or platelet count <50,000/mm³). During subsequent cycles complete blood count, differential, and platelet count will be obtained prior to each cycle. PT, PTT and fibrinogen will be obtained prior to each treatment phase.

Chemistries: During the first 3 cycles of treatment on each treatment phase ("A", "B"), obtain electrolytes, creatinine, calcium, magnesium, phosphorus, SGPT, and bilirubin every other week. During subsequent cycles these tests should be performed prior to each treatment cycle.

Urinalysis: Prior to treatment cycle 1, 4, 7, 10, and then q 6 cycles on each treatment phase ("A", "B").

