3.7 Post-Study Evaluation

The following tests and procedures should be performed, if possible, at the time a patient comes off study regardless of the reason for coming off study, unless the test or procedure has been performed in the past 6 weeks (2 weeks for physical examination and laboratory assessment).

- 3.7.1 HISTORY & PHYSICAL EXAMINATION (including a neurologic exam, performance status, and measurement of visible or palpable tumor lesions).
 - 3.7.2 Photographs of visible lesions (See Section 3.4.2)
 - 3.7.3 LABORATORY ASSESSMENT

Complete blood count, differential and platelet count, PT, and PTT. Electrolytes, creatinine, calcium, magnesium, phosphorus, SGPT, bilirubin. Urinalysis.

3.7.4 MRI Scan of the index lesions and any other progressing lesions using the protocol outlined in Appendix 1.

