APPENDIX 7: REQUIRED STUDY EVALUATIONS

Prior To Starting Treatment, During, And Post Treatment for Each Study Phase ("A" and "B"):

Observation	Pretreatment (Phase A&B)	During Cycle (Phase A&B)	Prior to Each Cycle (Phase A&B)	Post Study
History & physical exam	X	q 2 weeks, Cycles 1-3	Χ	Χ
Performance status	X		X (document if changed)	X
Body surface area	X		X	
Photography of lesions, if	X		Cycles 4, 7, 10, then q 6 cycles	Χ
possible				
CBC, platelets, differential	X	q 2 weeks, Cycles 1-3	X	X
PT, PTT, Fibrinogen	X		X	Χ
Electrolytes and creatinine	X	q 2 weeks, Cycles 1-3	X	Χ
Ca ⁺² , Mg ⁺² , PO ₄	X	q 2 weeks, Cycles 1-3	X	Χ
SGPT, bilirubin	X	q 2 weeks, Cycles 1-3	X	Χ
Urinalysis	X		Cycles 4, 7, 10, then q 6 cycles	Χ
Urine pregnancy test	Females			
3D-MRI of index lesions	Phase A only		Cycles 4, 7, 10, then q 6 cycles	Χ
Ophthalmologic examination	X			Χ
QOL assessment	Phase A only		Cycles 4, 7, 10, then q 6 cycles	
Tumor Biopsy	Phase A only	Between days 15-21, Cycle 1 Phase A and B		
PBMC for FPTase	Phase A only	Between days 15-21, Cycle 1		

Nerve growth factor Phase A only

Cycles 4, 7, 10, then q 6 cycles

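### No pregnancy test is scheduled while R115777 is being taken, in either arm, although treatment is open-ended and fetal risk is the stated reason for excluding pregnancy

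*Combined protocol and SAP*

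**What the plan says.** Sections 2.1.2.1 and 6.1 exclude pregnant patients because the risk to the fetus is unknown.

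The test itself is required in Section 2.2.6: "URINE PREGNANCY TEST: For all females of child-bearing potential". Section 2.2 extends the pre-treatment work-up to both phases: "The evaluation required prior to starting treatment phase 'A' and 'B' is listed in table form in Appendix 7". In Appendix 7 the row "Urine pregnancy test" has an entry only in the pretreatment column, which covers phases A and B. The during-cycle, pre-cycle and post-study columns are empty.

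Other assessments do continue on treatment. Section 3.4.3 schedules urinalysis "Prior to treatment cycle 1, 4, 7, 10, and then q 6 cycles on each treatment phase". Section 3.4.1 asks for history and examination every two weeks in the first three cycles, then: "After cycle 3 perform prior to each cycle". The off-study laboratory list in Section 3.7.3 ends "Electrolytes, creatinine, calcium, magnesium, phosphorus, SGPT, bilirubin. Urinalysis" and contains no pregnancy test.

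At crossover, Section 3.1.1 states: "There should be a 2 week washout period, during which no drug is administered, when crossing over from the first (phase A") to the second. Sections 3.1.3 and 8.1.9 let cycles continue until progression or another off-study criterion, with no maximum.

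**The concern.** The reason for the exclusion applies equally to a pregnancy that begins on treatment, yet testing stops once dosing starts. Patients aged 3 to 25 are eligible, so the trial will include females of child-bearing potential, and some girls may reach puberty during open-ended treatment.

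If sites follow the schedule exactly, a pregnancy that begins on R115777 is found only if the patient reports it, the clinician suspects it, or someone chooses to test. Recognition could be delayed by several cycles of a drug with unknown fetal effects. This is a matter of patient safety. It has no bearing on the power calculation or the primary comparison.

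**Working it through.** The plan gives no figure to reproduce here. The check sets the test schedule against the treatment sequence and then measures the untested time.

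**Scheduled tests by arm** (Sections 2.2, 3.1.1, 3.4.3, 3.7.3; Appendix 7)

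| | First test | Second test | Tests during R115777 |
|---|---|---|---|
| Arm 1 (R115777, then placebo) | Before R115777 | Before phase B, when R115777 has been stopped for crossover | 0 |
| Arm 2 (placebo, then R115777) | Before placebo | Before the first R115777 dose | 0 |

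The second test has value. In arm 2 it keeps a pregnant patient from starting R115777, and in either arm it would detect a phase A pregnancy still ongoing at crossover. In arm 1, however, it comes too late to shorten exposure. An arm 1 patient who leaves during phase A for toxicity or by choice never reaches it, and none is listed at exit. In arm 2 nothing follows it.

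**Length of untested treatment.** Cycles last 28 days (Section 3.1.3), so k cycles take 28 × k days and cycle k starts on day 28 × (k − 1).

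- The 12-month median hoped for in Section 5.4.2 is about 13 cycles: 13 × 28 = 364 days.
- Section 1.2.6 documents longer treatment: "Four patients with NF1 continue to receive R115777 on the 21 day schedule after a median of 19 (range 18-23) cycles". That is 18 × 28 = 504 to 23 × 28 = 644 days, with median 19 × 28 = 532 days. Thirteen NF1 patients entered on that schedule, so this is 4/13 = 31%.

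**Tests under three schedules.** The urinalysis dates are before cycles 4, 7, 10, 16 and 22 (days 84, 168, 252, 420 and 588). Testing before every cycle after the first gives k − 1 tests.

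| Cycles | Days | Present plan | On urinalysis dates | Before each cycle |
|---|---|---|---|---|
| 13 | 364 | 0 | 3 | 12 |
| 18 | 504 | 0 | 4 | 17 |
| 19 | 532 | 0 | 4 | 18 |
| 23 | 644 | 0 | 5 | 22 |

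The gaps are 3 × 28 = 84 and then 6 × 28 = 168 days on the urinalysis dates, and 28 days with testing before each cycle.

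**Wait for the crossover test in arm 1.** Assume exponential time to progression and ignore scan timing and withdrawals. The time remaining after a pregnancy begins then has the same median as the whole, and

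P(crossover test not yet reached after d days) = 2^(−d / median).

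The medians are those in Section 5.4.2: 6 months (182.6 days, no drug effect) and 12 months (365.25 days, the planned effect).

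| Days since pregnancy began | 6-month median | 12-month median |
|---|---|---|
| 84 | 2^(−84/182.6) = 0.727 | 2^(−84/365.25) = 0.853 |
| 168 | 0.529 | 0.727 |
| 252 | 0.384 | 0.620 |

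These are waits for the next scheduled test in a pregnancy not otherwise recognised. They are not estimates of time to detection.

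**The case against.** The exclusion is an entry criterion, the plan tests for it at entry and again before phase B, and nothing in the text promises testing in between. The right interval is a matter of judgement. Patients are examined at least once per cycle, with weight and body surface area recorded. They keep a diary of side effects, and investigators may test at any time. Sections 3.6.1 and 3.6.4 allow removal, and a birth defect is a reportable serious adverse event. Contraception and reporting instructions may be in the consent and assent forms, which were not available for this review. The 252-day row supposes a pregnancy unnoticed through about nine pre-cycle visits.

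Much of this is fair. There is no internal contradiction, and the visits make very long non-recognition less likely. The 252-day figures should be read only as time to crossover. The phase I patients show that long treatment happens; their sex is not reported. No window is given for the pre-phase-B test, so a site might do it at the progression visit.

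None of this supplies a scheduled test on R115777. Even at the progression visit, the drug is being stopped. Discretionary testing depends on suspicion, and Section 8.1.11 lists nausea, vomiting and fatigue as drug effects, so early signs of pregnancy could be put down to treatment. Reporting a birth defect comes after the exposure. Contraception advice, if given, is not a test.

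**Conclusion.** The concern holds. The number of scheduled pregnancy tests during R115777 exposure is zero in both arms, over treatment with no maximum length. At 13 cycles that is 364 days; at the durations seen in phase I it is 504 to 644 days. For an unrecognised pregnancy beginning in arm 1 phase A, the chance that the crossover test is still to come after 168 days is 53% to 73%, under the exponential assumption and the design medians. In arm 2 phase B no later test is scheduled at all.

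The count of zero rests on reading the pre-phase-B test as taking place once R115777 is being stopped, which is the natural reading. The number of females of child-bearing potential is not stated, so the number of pregnancies or fetal exposures cannot be estimated. No view is taken on contraception or notification duties. The gap should be closed on safety grounds.

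**What to change.** Add to Section 3.4.3, and to the pre-cycle column of Appendix 7, a urine pregnancy test for females of child-bearing potential before each treatment cycle in both phases. At minimum, run the test on the urinalysis specimens already collected before cycles 4, 7, 10 and every six cycles after that; this is weaker, because it still leaves gaps of up to 168 days. In Section 3.6.4, state that study drug is held on a positive test and stopped if pregnancy is confirmed.

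The cost is a short amendment, with matching consent and assent wording if it is not already there. Over 13 cycles each affected patient would have 12 urine tests, of which 12 − 3 = 9 fall at cycles without a urinalysis specimen; the minimum option needs 3 tests and no new specimens. No extra visit or invasive procedure is needed. The real burden is handling positive and false-positive results, including counselling and confidentiality for minors.
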